6.3 Statistical methods

Safety data will be analysed separately for maternal participants and their infant participants.

- Descriptive analysis

A flowchart will be used to summarise the number of mothers approached, consented, recruited, assigned to the different study arms, receiving the intended vaccines, completing the study protocol and analysed for the primary outcome, as recommended by the CONSORT statement (<http://www.consort-statement.org/>).

- Statistical significance and confidence intervals

A placebo controlled clinical trial investigating the safety and immunogenicity of GBS6 in pregnant women with and without human immunodeficiency virus (HIV) infection and their infants

Protocol Version 5.0, Dated 01/02/2023

Protocol Version/date 5.0,01/02/2023
R&D Protocol Code Number:
Page:33

MAKERERE UNIVERSITY
SCHOOL OF MEDICINE
APPROVED AMENDMENT
Valid Until

★ 30 NOV 2023 ★

RESEARCH & ETHICS COMMITTEE
[name]

5% significance will be used and 95% confidence intervals.

- Statistical software

Statistical analyses will be performed on STATA version 15 or similar.

- Missing data

Analysis will be by modified intention to treat (mITT), meaning individuals are analysed according to the group they are randomised to, but only those with at least one blood taken and antibody result will be included, with missing data (e.g. from withdrawals, non-compliers) assumed missing at random. Missing data will be excluded from relevant analyses. The mITT analysis will include blood samples taken outside the recommended timing. A per-protocol analysis will also be performed if there are major protocol deviations. Spurious data will be checked to source records and investigated but included if no cause is identified.

- Outliers, censored data and non-normal data

Outliers will be included in the analyses and investigated assuming no errors have occurred. We will assign all results of <2 a value of 1 for calculation of geometric means. Antibody concentrations will be log-transformed for analyses of mean antibody levels.

- Statistical analysis for each objective and outcome

Statistical Analysis of primary endpoints

The followings are the primary analyses for each of the outcomes related to primary objectives.

- Maternal primary endpoint 1:

Proportion of maternal participants reporting solicited local reactions within 7 days following administration of GBS6 vaccine will be calculated with exact binomial 95% confidence

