For each serotype, GBS serotype specific IgG GMT measured at baseline, and at delivery in HIV positive and HIV negative women will be calculated for each group with 95% confidence intervals. Groups 1 vs 2, 3 v 4 will be compared using similar methods to those for IgG concentrations.

- Infant secondary endpoint 1:

GMCs of GBS serotype specific IgG concentrations in HIV-exposed and unexposed infant participants measured at birth, 18 weeks and 12 months of life will be calculated at all blood draw visits for each group with 95% confidence intervals. Groups 1 vs 2, 3 v 4 will be compared using similar methods to those for maternal IgG concentrations.

- Infant secondary endpoint 2:

GMTs of GBS serotype specific IgG GMT in HIV-exposed and unexposed infant participants measured at 18 weeks of life will be calculated for each group with 95% confidence intervals. Groups 1 vs 2, 3 v 4 will be compared

- Infant secondary endpoint 3:

For each serotype, placental transfer ratio (infant GMC in cord blood or infant blood collected within 72 h of birth divided by maternal GMC in blood collected at delivery) will be calculated for each group with 95% confidence intervals. Groups 1 vs 2, 3 v 4 will be compared using similar methods to those for IgG concentrations.

Statistical analysis of exploratory endpoints

A placebo controlled clinical trial investigating the safety and immunogenicity of GBS6 in pregnant women with and without human immunodeficiency virus (HIV) infection and their infants

Protocol Version 5.0, Dated 01/02/2023

Protocol Version/date 5.0,01/02/2023
R&D Protocol Code Number:
Page:37

The followings are the primary analyses for each of the outcomes related to exploratory objectives.

- Maternal exploratory endpoint 1: The geometric mean fold ratio with a two-sided 95% CI will be calculated for group 4/group2. To account for differences between HIV positive and negative mothers the ratio of group 4/group 2 will be adjusted in a normal errors regression model on logged titers with terms included for covariates including maternal age, gestation and birth weight.

Maternal exploratory endpoint 2: Proportions of maternal participants with GBS colonisation assessed by vaginal and rectal swab before vaccination, at delivery, and 6 weeks after delivery will be calculated with exact binomial 95% confidence intervals for each group.

Comparison between groups (GBS v Placebo within each HIV strata) will be by Fisher's exact test.

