9.3. Patient randomisation

Participants will be randomized to either receive one dose of GBS6 vaccine or Placebo as a single injection on Day 1.

Stratified Block randomization will be used in this study. Randomization will be done in blocks of eight (8) in an automated system of Stata, stratified by HIV status and the list uploaded in the REDCap database. Participants will be randomized onto either arm (trial vaccine or placebo) of the study at enrolment by the data manager. The groups within REDCap will be labelled (A and B) and only the data manager will have access to the randomization

A placebo controlled clinical trial investigating the safety and immunogenicity of GBS6 in pregnant women with and without human immunodeficiency virus (HIV) infection and their infants

Protocol Version 5.0, Dated 01/02/2023

Protocol Version/date 5.0,01/02/2023
R&D Protocol Code Number:
Page:49

MAKERERE UNIVERSITY
SCHOOL OF MEDICINE
APPROVED AMENDMENT
Valid Until

★ 30 NOV 2023 ★

RESEARCH & ETHICS COMMITTEE
[name]

CRF, but the data manager will not be aware of which group (A or B) is the trial vaccine or placebo. Equal numbers will be allocated into each group (total n=300, 75 per group), with randomisation stratified by HIV status.

During the screening visit, the Data Manager will enter the participant's Screening ID into the REDCap system and complete the Randomization eCRF to randomise a participant. Once the participant is randomised, the REDCap system will randomly allocate the participant to either arm A or B as above. This will be notified automatically to the unblinded pharmacist. The unblinded pharmacist will take the notification and prepare the vaccine/placebo accordingly. The participants will use the same randomisation number throughout the study. The pharmacist will retain the lists of the allocation of unblinded medication prepared. The list must be kept in a safe place away from the blinded study team and will be monitored by the unblinded monitor.

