11.1.2 Visit 1- Vaccination (Day 1) Visit

- Review laboratory results.
- Ensure that the participant continues to be eligible for the study, meets none of the participants withdrawal criteria as described in Section 11.4, and meets none of the temporary delay criteria as described in Section 8.6.1.
- Prior to vaccination, measure vital signs, including weight, oral temperature, sitting blood pressure and pulse rate, and respiratory rate.

A placebo controlled clinical trial investigating the safety and immunogenicity of GBS6 in pregnant women with and without human immunodeficiency virus (HIV) infection and their infants

Protocol Version 5.0, Dated 01/02/2023

Protocol Version/date 5.0,01/02/2023
R&D Protocol Code Number:
Page:61

- Perform a targeted physical examination, evaluating any clinically significant abnormalities based on history and the participant's self-reported symptoms or complaints since the last visit.
- Perform obstetric examination including but not limited to fundal height, foetal heart tones, and foetal movement.
- Obtain urine sample for glucose and protein testing (urine dipstick).
- Issue the participant a paper diary card and provide instructions on its completion. Ensure that the participant records a baseline assessment of prompted systemic events in the paper diary card prior to vaccination.
- Prior to vaccination, collect a blood sample of approximately 10 mL for immunogenicity assessments and approximately 5 mL for CD4 count and viral load for HIV positive participants.
- Prior to vaccination, obtain one rectal and one vaginal swab for GBS microbiological culture.
- The unblinded dispenser dispenses the investigational product.
- The blinded administrator administers a single 0.5-mL injection of investigational product into the deltoid muscle, preferably of the nondominant arm.
- Blinded site staff must observe the participant for at least 30-minutes after investigational product administration for any acute reactions. Record any acute reactions in the participant's source documents and on the AE page of the CRF, and on an SAE form as applicable.
- Issue a measuring device to measure local reactions and a digital thermometer for recording daily temperatures, and provide instructions on their use.
- Ask the participant to complete the paper diary card from Day 1 to Day 7 (Day 1 is the day of vaccination).

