12.6. GBS Microbiological Cultures

One rectal and one vaginal swab will be collected from maternal participants at Day 1 (Visit 1), at delivery (Visit 4), and 6 weeks after delivery (Visit 6), and oral and rectal swabs will be obtained from their infant participants at birth and at 6 weeks (Visit 3) and 18 weeks (Visit 7) of age and cultured for GBS, to assess colonisation status.

Swab samples collected will be sent to Makerere University-Clinical Microbiology Laboratory, in Kampala, Uganda for GBS identification.

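### Minor, cheap improvement: the maternal colonisation comparisons at delivery and 6 weeks do not use each woman's pre-vaccination swab, which is valid but less efficient than a baseline-stratified test

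*Protocol*

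**What the plan says.** Section 6.3 introduces its exploratory methods with "The followings are the primary analyses for each of the outcomes related to exploratory objectives". For maternal exploratory endpoint 2 it gives exact binomial intervals per group for "Proportions of maternal participants with GBS colonisation assessed by vaginal and rectal swab before vaccination, at delivery, and 6 weeks after delivery", and adds: "Comparison between groups (GBS v Placebo within each HIV strata) will be by Fisher's exact test". No covariate, stratification by baseline result, or paired analysis is named for this endpoint.

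The swabs come from the same women. Section 12.6 states "One rectal and one vaginal swab will be collected from maternal participants at Day 1 (Visit 1), at delivery (Visit 4), and 6 weeks after" the birth. Section 11.1.2 puts the first of these before the injection: "Prior to vaccination, obtain one rectal and one vaginal swab for GBS microbiological culture".

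On level and size, section 6.3 says "5% significance will be used and 95% confidence intervals" and section 9.3 says "Equal numbers will be allocated into each group (total n=300, 75 per group), with randomisation stratified by HIV status". Section 6.1 calls the analyses largely descriptive and makes no power claim for colonisation. The end of section 6.3 leaves detailed and additional exploratory analyses to the SAP.

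**The concern.** A before-and-after binary outcome is available in every woman with readable swabs, but the named comparison looks only at group proportions. The text does not say that each visit is tested separately. That is an inference, though a Fisher test attached to three listed proportions has little other practical meaning.

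Three things follow if the text is applied as written.

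- The pre-vaccination proportions would be tested between randomised arms before any product is given. That null is true by design.
- The delivery and 6-week comparisons take no account of a chance imbalance in colonisation at Visit 1.
- Women already colonised at vaccination are pooled with women who were negative, so persistence and new acquisition are mixed in one proportion.

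At stake is some precision, and some clarity of interpretation, in an exploratory comparison that is already imprecise with 75 women per arm in each HIV stratum.

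**Working it through.** **Inputs from the protocol.** 75 v 75 within an HIV stratum (9.3); 5% level (6.3), taken as two-sided.

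**Inputs assumed, because the protocol gives none.** Placebo prevalence p of 20%, 30% or 40%, the same at Visit 1 and at follow-up; GBS6 halves colonisation; correlation phi between the Visit 1 and later results of 0, 0.3, 0.5 or 0.7. In the placebo arm the follow-up probability is p + phi(1 - p) if positive at Visit 1 and p(1 - phi) if negative. These differ by phi and average to p. In the GBS6 arm both are halved.

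**Step 1: the plan's own power figures.** Neither concerns colonisation, but both check the conventions.

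- Prematurity, 10% v 22%, 150 per arm: the null SE is sqrt(2 x 0.16 x 0.84/150) = 0.0423 and the alternative SE is sqrt((0.09 + 0.1716)/150) = 0.0418. Then z = (0.12 - 1.96 x 0.0423)/0.0418 = 0.89, so power is 81.2%.
- Antibody, 3.24-fold, SD 2.55, 75 per group: ln 3.24 = 1.176 and SE = 2.55 x sqrt(2/75) = 0.416. Then z = 1.176/0.416 - 1.96 = 0.86, so power is 80.6%.

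Both agree with the stated 80%, two-sided.

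**Step 2: colonisation, one HIV stratum, one post-vaccination visit.** Fisher and unadjusted chi-square power come from enumerating all tables. Mantel-Haenszel (MH) power, stratified by the Visit 1 result, comes from 100,000 simulated trials per cell.

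| Prevalence | Fisher | Chi-square | MH, phi 0 | MH, phi 0.3 | MH, phi 0.5 | MH, phi 0.7 |
|---|---|---|---|---|---|---|
| 20% | 32.3% | 41.0% | 40.1% | 42.4% | 47.0% | 56.8% |
| 30% | 52.7% | 60.1% | 59.8% | 62.6% | 68.3% | 77.6% |
| 40% | 71.4% | 76.8% | 76.7% | 79.2% | 83.8% | 90.8% |

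With no vaccine effect, Fisher rejects in 3.1-3.7% of trials and MH in about 5%.

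**Step 3: split the gain.**

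- Fisher to chi-square, which uses no baseline information: 8.7, 7.4 and 5.4 points. This part is Fisher's conservatism.
- Chi-square to MH, which is the baseline swab's own contribution: -0.9 to -0.1 at phi 0; 1.4 to 2.5 at phi 0.3; 6.0 to 8.2 at phi 0.5; 14.0 to 17.5 at phi 0.7.

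**Step 4: chance imbalance.** The SE of the Visit 1 difference is sqrt(2p(1 - p)/75), which is 6.5 points at p = 20% and 8.0 at 40%. A 10-point imbalance is therefore unremarkable. With no vaccine effect it shifts the expected follow-up difference by phi x 10, or 5 points at phi 0.5. Over repeated randomisation this averages to zero, so it is noise that the stratified test removes and not bias.

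**Step 5: low prevalence.** Section 5.2 defines the endpoint as serotype-specific, while section 6.3 analyses colonisation without naming serotype. At an assumed 5% per serotype and phi 0.5, power is 3.7% (Fisher), 11.4% (chi-square) and 12.3% (MH).

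**Step 6: baseline-positive women per arm and HIV stratum.** 75 x 0.20 = 15; 75 x 0.40 = 30; 75 x 0.05 = about 4.

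**The case against.** The strongest reply is that nothing here is wrong. An unadjusted Fisher test within a randomisation stratum is a valid comparison, the objective is only to characterise colonisation, no power is claimed, and section 6.3 leaves further analyses to the SAP. All of this stands and is why the point is minor. It does not remove the point: the protocol names the Fisher comparison as the primary analysis of this endpoint, and an additional SAP analysis would sit beside it. Adjustment is also already used in the same section, for maternal exploratory endpoint 1.

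A reader might infer more than the documents support:

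- That the baseline swab is unused. It is summarised per group with exact intervals; it is only absent from the post-vaccination comparisons.
- That acquisition and persistence cannot be separated. The data are collected and nothing prevents it.
- That the whole gap between Fisher and MH is the price of ignoring baseline. Step 3 shows that 5-9 points are Fisher's conservatism. Comparing Fisher with an exact test stratified by baseline does not isolate the swab's contribution either. At phi 0 the exact stratified test already gives 35.4% v 32.1% at 20% prevalence and 54.8% v 52.2% at 30%, through reduced discreteness alone.

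Two cautions about remedies also stand. Baseline-adjusted logistic regression targets a conditional odds ratio and not the proportions that the endpoint describes. Persistence estimates would rest on few women.

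**Conclusion.** The point holds as a minor, inexpensive improvement. The delivery and 6-week comparisons leave out a covariate measured in the same women, and a literal reading adds an uninformative test at Visit 1. Validity is not in question.

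The benefit cannot be sized from the documents. It is negligible if earlier and later colonisation are unrelated, small at phi 0.3, and material only from about 0.5. A positive correlation is plausible: vaccination at 27 0/7 to 35 6/7 weeks puts the first swab roughly 1 to 13 weeks before a delivery assumed at 37 to 40 weeks. The protocol does not document it. The figures also assume equal prevalence at both times, a halving of colonisation in both baseline groups, and no missing swabs. If the analysis is run by serotype at low prevalence, no choice of test gives useful power.

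**What to change.** In section 6.3, maternal exploratory endpoint 2:

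- Compare colonisation at delivery and at 6 weeks, separately and within each HIV stratum, by a Mantel-Haenszel (or exact stratified) test stratified by the Visit 1 swab result. Report the common risk difference with a 95% CI. With 1:1 allocation the Mantel-Haenszel weights nearly follow stratum size, so this stays close to the difference in overall proportions that the endpoint describes.
- Report the pre-vaccination proportions without a test.
- Report acquisition among women negative at Visit 1 and persistence among women positive at Visit 1 as counts and proportions only, because the positive groups are small.

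The cost is wording; all swabs are already scheduled. The one complication is that women without a readable Visit 1 result need a baseline-unknown stratum. The change should be fixed before unblinding, so that the choice of adjustment cannot depend on the results.

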8.1. Inclusion criteria for Maternal Participants

1. Age ≥ 18 to ≤ 40 years of age, inclusive at day of signing the ICF.
2. Pregnant at ≥ 27 0/7 to ≤ 35 6/7 gestation on the day of planned vaccination, verified by ultrasound scan (U/S).
3. Low risk, singleton pregnancy, as assessed by the study physician based on ultrasound scan and previous obstetric history.
4. Documented negative HBV surface antigen, HCV antibody, and syphilis tests at screening.
5. Normal full blood count (CBC), renal and liver function tests at screening.
6. Documented HIV test during pregnancy undertaken as per the national guidelines.
7. If HIV infected pregnant women, stable on ART for at least 2 months prior to study start with an undetectable viral load (VL)
8. Determined by medical history, physical examination, screening laboratory assessment, and clinical judgment to be appropriate for inclusion in the study.
9. Receiving prenatal standard of care including HIV care if applicable at the clinics/physician offices/hospital network affiliated with the clinical study site.
10. Willing to give birth at Kawempe Specialised National Referral Hospital, Kawaala or Komamboga Health Centre III or Wakiso or Kisenyi Health center IV, Uganda.

A placebo controlled clinical trial investigating the safety and immunogenicity of GBS6 in pregnant women with and without human immunodeficiency virus (HIV) infection and their infants

Protocol Version 5.0, Dated 01/02/2023

Protocol Version/date 5.0,01/02/2023
R&D Protocol Code Number:
Page:41

11. Willing and able to participate for the duration of the study visits and follow-up until 12-months post-delivery.
12. Willing and able to be contacted by telephone for the full duration of the study, and to give informed consent for their infant participant to participate in the study.

8.2. Inclusion criteria for Infants

Inclusion criteria for Infants

1. Parent(s) willing and able to comply with scheduled visits, investigational plan, laboratory tests, and other study procedures.

8.3. Exclusion criteria for Maternal Participants

Any of the following:

1. Investigator site staff members directly involved in the conduct of the study and their family members, site staff members otherwise supervised by the investigator, or participants who are Pfizer employees, including their family members, directly involved in the conduct of the study.
2. Participants whose unborn baby have been fathered by investigational site staff members directly involved in the conduct of the study or their family members, site staff members otherwise supervised by the investigator, or Pfizer employees directly involved in the conduct of the study.
3. Participation in other studies involving investigational drug(s), vaccines, or medical devices within 28 days prior to study entry and/or during study participation.
4. Previous vaccination with any licensed or investigational GBS vaccine.
5. History of severe adverse reaction associated with a vaccine and/or severe allergic reaction (e.g., anaphylaxis) to any component of the investigational product.
6. History of microbiologically proven invasive disease caused by GBS, or history of an infant with GBS disease.
7. Current alcohol abuse or illicit drug use.

A placebo controlled clinical trial investigating the safety and immunogenicity of GBS6 in pregnant women with and without human immunodeficiency virus (HIV) infection and their infants

Protocol Version 5.0, Dated 01/02/2023

Protocol Version/date 5.0,01/02/2023
R&D Protocol Code Number:
Page:42

8. Body mass index (BMI) of $\geq 40 \text{ kg/m}^2$ at the time of the screening visit.
9. Clinical history of primary genital herpes simplex virus (HSV) infection during the current pregnancy.
10. A prior history of or current pregnancy complications or abnormalities that will increase the risk associated with the participant's participation in, and completion of, the study, including but not limited to the following :

- a. Gestational hypertension or preeclampsia-eclampsia
- b. Placental abnormality
- c. Polyhydramnios or oligohydramnios
- d. Significant bleeding or blood clotting disorder
- e. Gestational diabetes
- f. Any signs of premature labour with the current pregnancy

11. Prior late stillbirth (defined as loss of pregnancy at any time after 28 weeks gestation) or neonatal death (defined as death of an infant within the first 28 days of life), prior low birth weight baby (defined as infant $< 2500 \text{ g}$) or premature delivery (defined as delivery before 37 0/7 weeks gestation), prior history of at least 3 miscarriages, prior pregnancies numbering greater than 5, or previous infant with a known or suspected genetic disorder or major congenital anomaly

12. Confirmed GBS bacteriuria during the current pregnancy

13. Major illness of the mother (outside of HIV serostatus) or conditions of the foetus that, in the investigator's judgment, will substantially increase the risk associated with the participant's participation in, and completion of, the study or could preclude the evaluation of the participant's response, including but not limited to the following:

- a. hypertension requiring treatment
- b. heart disease
- c. lung disease
- d. neurological disorders including a history of epilepsy or recurrent afebrile seizures

A placebo controlled clinical trial investigating the safety and immunogenicity of GBS6 in pregnant women with and without human immunodeficiency virus (HIV) infection and their infants

- e. kidney disease
- f. liver disease
- g. haematological disorders (including sickle cell disease)
- h. severe anaemia (less than 7.0g/dL)
- i. significant bleeding or blood clotting disorder
- j. endocrine disorders including known diabetes mellitus

14. Participants with known or suspected immunodeficiency (outside of HIV positive sero-status).

15. Participants who receive treatment with immunosuppressive therapy including cytotoxic agents or systemic corticosteroids, e.g., for cancer or an autoimmune disease, or planned receipt through the postvaccination blood draw. Inhaled/nebulised, intra-articular, intra-bursal, or topical (skin or eyes) corticosteroids are permitted.

16. Receipt of blood/plasma products or immunoglobulin, from 60 days before investigational product administration, or planned receipt through delivery.

17. Known to be Rhesus Negative

18. Psychiatric condition including recent (within the last year) or active suicidal ideation or behaviour or laboratory abnormalities that may increase the risk associated with study participation or investigational product administration or may interfere with the interpretation of study results and, in the judgment of the investigator, would make the participant inappropriate for entry into this study.

19. Deprived of freedom by an administrative or court order, or in an emergency setting, or hospitalised involuntarily.

